2.3.7 Follow-up Period

Efficacy and safety endpoints will be determined in all patients at each scheduled visit over the 24-month follow-up period (planned at 1, 3, 6, 12, 18, and 24 months).

[figure not shown]
2.4 Long -Term Follow-up

A long-term follow-up will be performed via phone calls at 36 and 48 months after IMP implantation. This includes assessment of hip symptoms (pain, stiffness, and function) using WOMAC® LK3.1 (Likert Scale), radiological progression (conventional X-ray to be performed only when the patient still feels pain on the treated hip) and the potential occurrence of any AEs and SAEs (patient open questionnaire, including notably any changes in health status and need for total hip arthroplasty).

3 DETAILED SCHEDULE OF VISITS AND PROCEDURES

An overview of the study assessments and procedures is given in the Flow Chart below. Study procedures are described separately for the PREOB® study and the long term follow-up in table 2 and table 3 respectively. These Tables show how efficacy and safety endpoints relate to the study objectives, and describe involvement of the Investigator (in white), Independent Physician (in red), and Central Radiologist (in blue).

Figure 1: Study Flow-Chart

*In case V1A and V1B are performed separately: X-ray shall be performed during visit 1A. If >4 weeks have elapsed between the 2 visits, X-Ray must be repeated at V1B, only.

[‡]Procedure performed by the Independent Physician (UNBLIND). Principal Investigator and other staff members are BLIND.

PREOB-ON3 - Clinical Study Protocol

PREOB-ON3-CSP

V 6.1

Author: [name]

May 15, 2017

Pg. 44/45

Table 2: Follow-up Period: Schedule of visits and procedures

PREOB-ON3 - Clinical Study Protocol

PREOB-ON3-CSP

V 6.1

Author: [name]

May 15, 2017

Pg. 45/46

Table 3: Long Term Follow-up: schedule of phone calls and procedures

Visits	Long term follow-up	
	Month 36	Month 48
	Visit 10	Visit 11

PREOB-ON3 - Clinical Study Protocol

PREOB-ON3-CSP

V 6.1

Author: [name]

May 15, 2017

Pg. 46/47

3.2 Randomisation

In case of patient eligibility,

- Randomisation is performed by the Principal Investigator (or delegate) through the eCRF.
- The eCRF will automatically allocate a unique Randomisation Number for the patient.
- Upon randomisation, the eCRF will automatically inform the study team that a new patient has been randomised.

PREOB-ON3 - Clinical Study Protocol

PREOB-ON3-CSP	V 6.1	Author: [name]	May 15, 2017	Pg. 48/49
---------------	-------	----------------	--------------	-----------

- Both the unblind Independent Physician and the Sponsor's Managing Physician must log into the eCRF system to obtain the patient's treatment allocation.

3.3 (Sham) Bone Marrow Harvest and Blood Collection (Visit 2, Day -21)

The (sham) bone marrow harvest and blood collection (Visit 2, Day -21) will be performed at least **21 days**⁴ before the Core decompression/implantation procedure (Visit 3, Day 0).

Before the actual (sham) bone marrow harvest and blood collection procedures, the following evaluations must be performed either by the Independent Physician or by the Principal Investigator (or delegate):

[REDACTED]

The (sham) bone marrow harvest and blood collection procedures must be conducted by the Independent Physician exclusively:

(Sham) Bone Marrow Harvest procedure (see detailed description in Section 4.1) will be performed by the Independent Physician. (Sham) bone marrow and blood samples will then be immediately labelled and packed by the Independent Physician *himself*, and immediately shipped to the Sponsor's Manufacturing Unit for further processing (see detailed description of packaging, labelling, and shipment procedures in Study Procedure Manual (SPM) for IP).

⁴ The bone marrow harvest and the core decompression procedure will be scheduled in conjunction with the Sponsor's Manufacturing Unit and will take into account the travel time between the Investigating Site and the Sponsor's Manufacturing Unit.

**PREOB-ON3 - Clinical Study Protocol**

PREOB-ON3-CSP

V 6.1

Author: [name]

May 15, 2017

Pg. 49/50

Patients will then be allowed to leave the Clinic on the same day, following thorough clinical evaluation and documentation of any potential AEs or SAEs.

3.4 Product Implantation (Visit 3, Day 0 and Day +1)**Day 0**

The patient will be admitted to the Clinic on Day 0. The following examinations and procedures will then be performed by the Investigator:

[REDACTED]

[REDACTED]

[REDACTED]

[REDACTED]

[REDACTED]

[REDACTED]

[REDACTED]

On the same day, the shipping box containing the Investigational Medicinal Product (PREOB® or Placebo) will be shipped by the Manufacturer to the Pharmacy Department of the Investigating Site.

If the IMP is not useable due to a technical problem that occurred during the production process, the Managing Physician will immediately notify the CAs and SSO, and record relevant information in the eCRF. Once completed, the eCRF will automatically send e-mail alerts to the Study Safety Officer (SSO), and PI.

In case the IMP is not available for the implantation, the PI will inform the patient about the cancellation of the latter procedure. In this case, the patient will be considered as drop out, but the Investigator is however allowed to re-include the patient after 2 months (novel inclusion procedure).

Upon IMP receipt the Pharmacist will check if all the conditions listed on the Release Form for the Hospital - Hospital Pharmacist Section - are met, and subsequently release the IMP and immediately inform the Principal Investigator (and/or delegate) (see detailed description of related procedures in the SPM for Pharmacist). If released by the pharmacist, the IMP will be transferred to the Operating Room.

PREOB-ON3 - Clinical Study Protocol

PREOB-ON3-CSP

V 6.1

Author: [name]

May 15, 2017

Pg. 50/51

In the Operating Room, the Principal investigator will check if all the conditions listed on the Release Form for the Hospital - Principal Investigator Section - are met, and subsequently release the IMP and perform the surgical procedure (core decompression and implantation, PREOB® or Placebo) (see detailed procedures in Section 4.2 and in the SPM for PI).

After implantation, the empty PREOB® or Placebo syringe will be kept and stored by the Investigator (or a member of the investigating team designated by the Investigator) until the next Monitoring visit.

Day +1

Patients will be systematically evaluated 24 hours after the core decompression/implantation procedure, and will then be discharged from the Clinic after the following examinations:

[REDACTED]

[REDACTED]

[REDACTED]

[REDACTED]

[REDACTED]

[REDACTED]

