The full analysis set (FAS) consists in an modified Intention-To-Treat population and will be considered as the primary cohort for analysis of efficacy.

The superiority of PREOB® over Placebo will be considered achieved if the percentage of treatment responders is statistically significantly higher in the PREOB® group than in the Placebo group at Month 24. The primary efficacy endpoint will be compared between the two groups by means of a Chi square or a Fisher's exact test (as appropriate). The difference between the two groups will be considered significant if the *p*-value is less than or equal to the Type I error.

Comparison between treatment groups of the secondary binary efficacy endpoints will be performed at each studied timepoint, by means of a Chi square test or a Fisher's exact test (as appropriate). Treatment effect over the 24-month follow-up period will be assessed using a Generalized Estimating Equations (GEE) model taking into account correlations between the repeated measurements within patients.

Comparisons between treatment groups of the secondary continuous efficacy endpoints will be performed at each studied timepoint by means of a parametric Student t-test or a non-parametric Wilcoxon rank-sum test (as

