VAS	Visual Analogue Scale
WHO	World Health Organization
WOMAC®	Western Ontario McMaster University Score®
WMA	World Medical Association

PREOB-ON3 - Clinical Study Protocol

PREOB-ON3-CSP	V 6.1	Author: [name]	May 15, 2017	Pg. 18/19
---------------	-------	----------------	--------------	-----------

DEFINITIONS

- **Approval (in relation to ethics committees (ECs)):** the affirmative decision of the EC that the clinical trial has been reviewed and may be conducted at the investigating site within the constraints set forth by the EC, the Institution, Good Clinical Practice (GCP, and the applicable regulatory requirements.
- **Autologous:** means that the donor of the human biological material and the recipient of the investigational medicinal product (IMP) is the same individual.
- **Case report form (CRF or eCRF):** a printed, optical, or electronic document designed to record all of the protocol-required information to be reported to the Sponsor on each trial subject.
- **Clinical study:** is any investigation in human subjects intended to discover or verify the clinical, pharmacological and/or other pharmacodynamic effects of an investigational medicinal product and/or to identify any adverse reactions to an investigational medicinal product, and/or to study absorption, distribution, metabolism, and excretion of an investigational medicinal product with the object of ascertaining its safety and/or efficacy - PREOB® in this case.
- **Completed patient:** a patient who completed all scheduled visits up to last scheduled visit (inclusive).
- **Contract Research Organization (CRO):** a person or an organization contracted by the Sponsor to perform one or more of the Sponsor's trial-related duties and functions.
- **Data Safety Monitoring Board (DSMB):** an independent data monitoring committee established by the Sponsor to assess at intervals the progress of a clinical trial, the safety data, and the critical efficacy endpoints, and to recommend to the Sponsor whether to continue, modify or stop the trial.
- **Discontinued or withdrawn patient:** a patient who has been enrolled, screened, randomised or treated but has withdrawn from the study before completion of the last scheduled visit.
- **Drop out:** a patient who has been randomised but never treated.
- **Distribution:** transportation and delivery of tissues and cells intended for human applications.
- **Eligible patient:** a screened patient who is considered eligible according to selection criteria.

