- **Mesenchymal stromal (stem) cells (MSC):** “plastic-adherent” stem cells, expressing specific surface markers, and giving rise to bone, cartilage, and adipocyte cells.
- **Monitor:** refers to Sponsor's authorized CROs and/or CRAs.
- **Multicenter Trial:** a clinical trial conducted according to a single protocol but at more than one site, and, therefore, carried out by more than one investigator.
- **Non-traumatic osteonecrosis:** a bone disease characterized by necrosis of bone and medullary tissues, mainly at bone epiphyseal sites evolving towards articular collapse and joint destruction due to non-traumatic aetiological factors.
- **Osteoblastic cells:** cells belonging to the osteoblastic lineage (bone forming cells) encompassing the osteoprogenitors, the pre-osteoblasts, the osteoblasts, the lining cells and the osteocytes.
- **Patient:** an individual participating in the clinical trial.
- **PREOB®:** a proprietary autologous osteoblastic cells (PREOB® cells) product, *i.e.*, an advanced therapy medicinal product falling under the scope of the European Regulation 1394/2007/EC and the Directive 2001/83/EC manufactured by Bone Therapeutics S.A.
- **Processing:** all operations involved in the preparation, manipulation, preservation, and packaging of tissues or cells intended for human applications.
- **Procurement:** a process by which tissues or cells are made available.
- **Production/Tissue Establishment:** a tissue bank or a unit of a hospital or another body where activities of procurement, testing, processing, preservation, storage, and/or distribution of human tissues and cells are undertaken.
- **Randomised patient:** a patient to whom a randomisation number has been allocated.

PREOB-ON3 - Clinical Study Protocol

PREOB-ON3-CSP	V 6.1	Author: [name]	May 15, 2017	Pg. 20/21
---------------	-------	----------------	--------------	-----------

- **Screened patient:** a patient who has dated and signed the Informed Consent Form (ICF) (enrolled patient) and who has performed the checking of the selection criteria.
- **Screening failure:** a screened patient who is not eligible for the study after checking the selection criteria.

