4 DETAILED DESCRIPTION OF THE PROCEDURES AND INVESTIGATIONAL MEDICINAL PRODUCT

Site staff will be trained on the trial-related procedures and Standard Operating Procedures, including step-by-step instructions during the Site Initiation Visit (SIV) at the latest.

Table 4: Summary of Procedures Performed in the PREOB® and Placebo Groups

Procedures	Timepoints	PREOB® Group	Placebo Group
Bone Marrow Harvest	Day-21	Yes [REDACTED]	Yes [REDACTED]
Peripheral Blood Sampling	Day-21	Yes [REDACTED]	Yes [REDACTED]
Core decompression (using a 5mm trephine)	Day 0	Yes	Yes
Intra-osseous Implantation (blind vials)	Day 0	Yes	Yes

4.1 Bone Marrow Harvest and Blood Collection Procedures (performed by the Independent Physician)

PREOB® Group - Bone Marrow Harvest Procedure

At least twenty-one days⁵ before the surgical procedure (Implantation Visit, Visit 3), the patient will be admitted to the hospital in order to undergo a bone marrow aspiration (Visit 2). In the operating room or another aseptic environment, the patient will be placed on the left or right side (on the target hip side or not, as judged by the Independent Physician), and local anaesthesia of the skin, muscles, and periosteum of the right or left posterior iliac crest will be performed using 5-10 ml of a local anaesthetic (e.g., lidocaïn hydrochloride). Sedation can be administered as per Independent Physician judgement. After 5 to 10 minutes, a 5-mm incision will be made at the level of the posterior iliac crest, the bone marrow aspiration needle is introduced into the iliac crest, and [REDACTED] bone marrow is aspirated and used for the culture of PREOB®. If the bone marrow harvesting is difficult or insufficient, the orientation of the needle within the same incision can be modified according to the need. The patient will then be placed in a supine position and [REDACTED] peripheral blood will be taken. The patient will be

⁵ The bone marrow harvest and the core decompression procedure should be scheduled in conjunction with the Sponsor's Manufacturing Unit and should take into account the travel time between the Investigating Site and the Sponsor's Manufacturing Unit.

PREOB-ON3 - Clinical Study Protocol

PREOB-ON3-CSP	V 6.1	Author: [name]	May 15, 2017	Pg. 55/56
---------------	-------	----------------	--------------	-----------

allowed to leave the hospital 30 minutes after vital signs have been checked (see detailed procedures in the SPM for the Independent Physician).

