Control Group - Sham Bone Marrow Harvest Procedure

At least twenty-one days⁶ before the surgical procedure (Implantation Visit, Visit 3), the patient will be admitted to the hospital in order to undergo a sham bone marrow aspiration (Visit 2). In the operating room or another aseptic environment, the patient will be placed on the left or right side (on the target hip side or not, as judged by the Independent Physician), and local anaesthesia of the skin, muscles, and periosteum of the right or left posterior iliac crest will be performed using 5-10 ml of a local anaesthetic (e.g., lidocaïn hydrochloride). Sedation can be administered as per Independent Physician judgement. After 5 to 10 minutes, a 5-mm incision will be made at the level of the posterior iliac crest, and the bone marrow aspiration needle is placed in contact with the iliac crest for 5 minutes without penetration of the bone. There will be no bone marrow aspiration. The patient will then be placed in a supine position for 10 minutes and [REDACTED] peripheral blood will be taken. The patient will be allowed to leave the hospital 30 minutes after vital signs are checked (see detailed procedures in the SPM for the Independent Physician).

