In case the IMP is not available for the implantation, the Investigator will inform the patient about the cancellation of the procedure. In this case, the patient will be considered as drop out, but the Investigator is however allowed to re-include the patient after 2 months (novel inclusion procedure).

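### PREOB patients whose culture fails after randomisation, and who are not later re-included and treated, fall outside all three analysis sets; the protocol states no all-randomised analysis and no allocation rule for re-inclusion

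*Combined protocol and SAP*

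**What the plan says.** **Order of events.** Section 3.2 places randomisation before the harvest visit: "The eCRF will automatically allocate a unique Randomisation Number for the patient". Section 4.1 then separates the arms. In the PREOB group "bone marrow is aspirated and used for the culture of PREOB"; in the control group the harvest is a sham: "There will be no bone marrow aspiration".

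**When the product is unavailable.** Section 3.4 foresees a technical problem in production. Where there is no product for implantation, the procedure is cancelled and: "In this case, the patient will be considered as drop out, but the Investigator is however allowed to re-include the patient after 2 months". It describes re-inclusion as a novel inclusion procedure, and section 4.2.1 repeats the rule. The Definitions describe a drop out as "a patient who has been randomised but never treated" and a randomised patient as "a patient to whom a randomisation number has been allocated".

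**Analysis sets.** Section 10.5 names three. The safety set needs both core decompression and implantation. The full analysis set (FAS) needs randomisation, treatment, and baseline and post-baseline values of ARCO stage and WOMAC pain. The per-protocol set is a subset of the FAS. Of the FAS, the synopsis says that it "will be considered as the primary cohort for analysis of efficacy". The FAS is analysed by randomisation group, the safety set by product received.

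**Where further detail is deferred.** The synopsis and the opening of section 10 make a separate SAP the reference for statistical methods and say that the protocol's description is not exhaustive.

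**The concern.** Treatment status is settled after randomisation, and one of the ways to remain untreated exists in one arm only. A set restricted to treated patients then no longer has the protection of randomisation on that point. If PREOB patients whose cells fail to grow would have responded less often than the rest, removing them raises the PREOB rate, while patients of the same kind stay in the placebo arm. If they would have responded more often, the effect is reversed.

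Missing-data rules applied within the FAS cannot repair this, because the patient is not in the FAS.

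Re-inclusion adds a second gap. The protocol does not say whether the person keeps the first allocation or draws a new one, or whether one person counts once or twice. Analysis by randomisation group has no single meaning for someone randomised twice.

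**Working it through.** **1. The plan's own figure.** Section 10.4 gives 63% v 30%, two-sided 5%, 90% power, chi-square test.

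n per arm = [1.960·√(2·0.465·0.535) + 1.282·√(0.63·0.37 + 0.30·0.70)]² / 0.33² = 45.9, so 46, as stated.

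Next, 1.19 × 92 = 109.5, so 110. Then 110/0.925 = 118.9 against the stated 118; since 118 × 0.925 = 109.2, this is consistent with the plan's aim of around 110 evaluable patients. Nothing here needs correcting. The 7.5% allowance covers numbers and says nothing about balance between the arms.

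**2. Which set holds an untreated patient.**

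| Set (10.5) | Requires treatment? | Product unavailable, never re-included | Re-included and treated |
|---|---|---|---|
| Safety | yes | out | in, by product received |
| FAS | yes | out | in if the value requirements are met; which allocation is not stated |
| Per-protocol | yes (subset of FAS) | out | in if in the FAS and without major deviation |

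**3. Shift from exclusion alone.** Let f be the share of the PREOB arm that fails in culture and d the response rate of other patients minus that of failures. With no true effect, placebo keeps both kinds of patient and the PREOB FAS keeps only the others:

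shift = p_others − [(1−f)·p_others + f·p_failures] = f·d.

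The documents give neither f nor d. Assumed ranges:

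| | d = 15 points | d = 30 points |
|---|---|---|
| f = 5% | 0.75 | 1.5 |
| f = 15% | 2.25 | 4.5 |

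So the shift is 0.8 to 4.5 points after rounding. It favours PREOB if failures respond less often and placebo if more often, and is 0 when d = 0. These are illustrations, not limits.

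**4. Bias of the all-randomised alternatives.** Take no true effect, 30% response overall, and failures who respond at rate p.

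- Failures scored as non-responders: bias = −f·p. At p = 30% this is −1.5 to −4.5 points (f = 5% to 15%); at p = 0 it is 0.
- Failures given the placebo rate: bias = f·(0.30 − p). At p = 30% it is 0; at p = 0 it is +1.5 to +4.5 points.

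Under no effect the two versions bracket the truth when p lies between 0% and 30%. Neither is unbiased in general, and p above 30% needs rates above the placebo rate.

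**5. Power of the all-randomised analysis.** Simulation of 1,000,000 trials: chi-square test, 0.01341 per tail (section 10.7) at 24 and 59 per arm, the same endpoint assumed at both looks, placebo 30%, no loss to follow-up. PREOB rate: 0.63(1−f) for the non-responder version, 0.63(1−f) + 0.30f for the placebo-rate version.

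| PREOB-only failure | Non-responder: rate, power | Placebo-rate: rate, power |
|---|---|---|
| 0% | 63.0%, 94% | 63.0%, 94% |
| 5% | 59.9%, 88% | 61.4%, 91% |
| 10% | 56.7%, 80% | 59.7%, 88% |
| 15% | 53.6%, 69% | 58.1%, 84% |

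If a further 5% of each arm (assumed) is lost and scored as non-response, the non-responder version falls to about 85%, 76% and 65% at 5%, 10% and 15% failure.

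**The case against.** **The unseen SAP.** The protocol defers its statistical detail to the SAP, which could add an all-randomised analysis, a disposition table by arm or a counting rule. This stands. A reader might infer that the effect of exclusions could never be judged from the trial's reports; the documents do not support that. They show only that the protocol promises none of these. The allocation of a re-included patient is also a rule of conduct that sites need in the protocol.

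**Re-inclusion.** A reader might infer that every patient without product is lost to the analysis. That is wrong: someone re-included and treated enters the safety set, and the FAS if the values exist. The exclusion concerns those never re-included.

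**Both arms can fail.** A reader might infer that exclusion happens only under PREOB. The unavailability rule covers both arms, and placebo also has a manufacturer, a batch and a release step. Only the culture step is one-sided.

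**No link to prognosis.** A reader might infer that the result will be biased towards PREOB. No passage ties culture failure to response. Section 1.2 reports no significant difference in yield by aetiology, which does not bear on yield and response. Its account of reduced cell proliferation in osteonecrosis makes a link conceivable and no more.

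**The top of the range.** A 15% failure rate in one of two equal arms is 7.5% of all randomised patients, the whole allowance in section 10.4 for drop-out and loss together. A 30-point deficit from about 30% means that almost no failure would respond. The 4.5-point figure is therefore an extreme case relative to the plan.

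**Numbers and naming.** Drop-outs are allowed for in the sample size and the cohort is openly called modified intention-to-treat. Both are true; neither deals with exclusion that depends on the arm. A reader might also see a contradiction with the no-replacement rule in section 9.3, but that section speaks of withdrawn patients and does not plainly conflict.

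**Conclusion.** The point holds in a limited form, with medium confidence. As the protocol is written, the primary FAS comparison permits post-randomisation exclusion that can depend on the arm, through culture failure in PREOB patients who are not re-included and treated. The allocation and counting of a re-included patient are not stated, and neither is an all-randomised analysis.

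Whether bias arises, and in which direction, cannot be determined from the documents. The illustrative 0.8 to 4.5 points rests on assumed failure rates and response gaps and on no true effect. It is small beside the planned 33 points and does not by itself threaten a result of that size. It should be fixed because this is a pivotal trial and the remedy is cheap.

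**What to change.** 1. **Section 10.5 and the SAP.** Keep the FAS as the primary cohort. Pre-specify a sensitivity analysis of all randomised patients by first allocation, each person counted once. Use the observed Month 24 outcome for anyone re-included and treated. For never-treated patients report a range of assumed response rates: non-response, the placebo-arm rate, and rates above it. Do not describe the non-responder version as unbiased.
2. **Reporting.** Tabulate production failures, all other never-treated patients and all re-included patients by arm of first allocation.
3. **Re-inclusion.** In sections 3.4 and 4.2.1 state whether a re-included patient keeps the first allocation, and in section 10.5 under which allocation that person enters the FAS. Keep the safety set by product received.

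The cost is wording in the protocol and SAP and one more table. No new patients are needed while the all-randomised result is a sensitivity analysis. The downside is a less favourable supporting figure, with the power shown above for the non-responder version and less if patients are lost to follow-up. If re-inclusion draws a new arm, analysis by first allocation dilutes the difference further, which is why the number of re-included patients must be reported.
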